#### 8.6. Unscheduled Visits

Unscheduled visits may occur as clinically indicated. They can be used for visits that occur outside of visit windows and should be noted in the eCRF as an unscheduled visit.

#### 8.7. End of Treatment

When the participant permanently discontinues study treatment, whether the participant is terminating the study early or the participant has completed the study, the EOT visit should be

conducted. If the EOT visit coincides with a regular study visit, the EOT evaluations will supersede those of that scheduled visit, and the data should be entered in the EOT visit in the eCRF. The participant should be encouraged to return for the follow-up visit.

## **8.8. Follow-Up**

### **8.8.1. Safety Follow-Up**

The safety follow-up period is the interval between the EOT visit and the scheduled follow-up visit, which should occur 30 to 35 days after the EOT visit (or after the last dose of study treatment if the EOT visit was not performed). Adverse events and SAEs must be reported up until 1) at least 30 days after the last dose of study treatment, the date of the follow-up visit, or the start of a new anticancer therapy or 2) until toxicities resolve, return to baseline, or are deemed irreversible, whichever is longer. Reasonable efforts should be made to have the participant return for the follow-up visit and report any AEs that may occur during this period. If the participant cannot return to the site for the safety follow-up visit (eg, lives far away), the participant should be contacted by telephone for assessment of AEs and SAEs. Sites should document this contact in the source.

If a participant is scheduled to begin a new anticancer therapy before the end of the 30- to 35-day safety follow-up period, the safety follow-up visit should be performed before the new anticancer therapy is started. Once new anticancer therapy has been initiated, the participant will move into the survival follow-up period.

### **8.8.2. Post-Treatment Disease Follow-Up**

Participants who discontinue study treatment for a reason other than disease progression will move into the disease status follow-up period and should be assessed every 9 weeks  $\pm$  7 days by radiologic imaging to monitor disease status. Every effort should be made to collect information regarding disease status until:

- The start of new anticancer therapy: the start of the new treatment should be captured, but the participant should continue to have disease assessments until progressive disease (see below).
- Disease progression (confirmed by an ICR).
- Death.
- The end of the study.

### **8.8.3. Survival Follow-Up**

Once a participant has received the last dose of study treatment, confirmed disease progression, or starts a new anticancer therapy, the participant moves into the survival follow-up period and should be contacted by telephone, email, or visit at least every 12 weeks to assess for survival status until death, withdrawal of consent, or the end of the study, whichever occurs first.

For participants having entered the survival follow-up period of the study, the site will use continuing participant records to supply data on subsequent treatment regimens, tumor assessments (if discontinued treatment for a reason other than progression), and OS in the eCRF. For participants who do not intend to return to the study investigator for their ongoing care, follow-up should be maintained by phone contact, patient records, and public records/databases approximately every 12 weeks.

## **9. ADVERSE EVENTS: DEFINITIONS AND PROCEDURES FOR RECORDING, EVALUATING, FOLLOW-UP, AND REPORTING**

### **9.1. Definition of Adverse Event**

Adverse Event Definition

• An AE is any untoward medical occurrence associated with the use of a drug in humans, whether or not considered drug-related.

• An AE can therefore be any unfavorable and unintended sign (including an abnormal laboratory finding), symptom, or disease (new or exacerbated) temporally associated with the use of study treatment.

Events Meeting the Adverse Event Definition

• Any safety assessments (eg, ECG, vital signs measurements), including those that worsen from baseline, considered clinically significant in the medical and scientific judgment of the investigator (ie, not related to progression of underlying disease).

• Abnormal laboratory test results constitute an AE if they are considered clinically meaningful, induce clinical signs or symptoms, require concomitant therapy, or require changes in study drug. Whenever possible, a diagnosis (eg, anemia, thrombocytopenia) should be recorded in the eCRF rather than the abnormal laboratory result (eg, low hemoglobin, platelet count decreased).

• Exacerbation of a chronic or intermittent pre-existing condition including either an increase in frequency and/or intensity of the condition.

• New conditions detected or diagnosed after study treatment administration even though they may have been present before the start of the study.

• Signs, symptoms, or the clinical sequelae of a suspected drug-drug interaction.

• Signs, symptoms, or the clinical sequelae of a suspected overdose of either study treatment or a concomitant medication. Overdose per se will not be reported as an AE/SAE unless it is an intentional overdose taken with possible suicidal/self-harming intent. Such overdoses should be reported regardless of sequelae.

Events NOT Meeting the Adverse Event Definition


• Any clinically significant abnormal laboratory findings or other abnormal safety assessments that are associated with the underlying disease, unless judged by the investigator to be more severe than expected for the participant's condition.

• The disease/disorder being studied or expected progression, signs, or symptoms of the disease/disorder being studied, unless more severe than expected for the participant's condition or considered to be treatment-related by the investigator.

- Efficacy endpoints as outlined in Section 3 will not be reported as AE/SAEs, specifically, any event that is related to disease progression of the cancer under study. Unblinded aggregated efficacy endpoint events and safety data will be monitored to ensure the safety of the participants in the study. Any suspected endpoint that upon review is not progression of the cancer under study will be forwarded to Incyte Pharmacovigilance as a SAE within 24 hours of determination that the event is not progression of the cancer under study.
- Medical or surgical procedure (eg, endoscopy, appendectomy): the condition that leads to the procedure is the AE if it occurred after signing informed consent. If present before entering the study, the condition should be captured as medical history.
- Situations in which an untoward medical occurrence did not occur (social and/or convenience admission to a hospital).
- Anticipated day-to-day fluctuations of pre-existing disease(s) or condition(s) present or detected at the start of the study that do not worsen.

## 9.2. Definition of Serious Adverse Event

If an event is not an AE per definition above, then it cannot be an SAE even if serious conditions are met (eg, hospitalization for signs/symptoms of the disease under study, death due to progression of disease).

A Serious Adverse Event is defined as any untoward medical occurrence that, at any dose:
a. Results in death
b. Is life-threatening
The term 'life-threatening' in the definition of 'serious' refers to an adverse drug experience that places the participant, in the opinion of the initial reporter, at immediate risk of death from the adverse experience as it occurred. This does not include an adverse drug experience that, had it occurred in a more severe form, might have caused death.
c. Requires inpatient hospitalization or prolongation of existing hospitalization
In general, hospitalization signifies that the participant has been detained (usually involving at least an overnight stay) at the hospital or emergency ward for observation and/or treatment that would not have been appropriate in the physician's office or outpatient setting. Complications that occur during hospitalization are AEs. If a complication prolongs hospitalization or fulfills any other serious criteria, the event is serious. When in doubt as to whether "hospitalization" occurred or was necessary, the AE should be considered serious.
Hospitalization for elective treatment of a pre-existing condition that did not worsen from baseline is not considered an AE.
d. Results in persistent or significant disability/incapacity

• The term disability means a substantial disruption of a person's ability to conduct normal life functions.

• This definition is not intended to include experiences of relatively minor medical significance, such as uncomplicated headache, nausea, vomiting, diarrhea, influenza, and accidental trauma (eg, sprained ankle), that may interfere with or prevent everyday life functions but do not constitute a substantial disruption.

e. Is a congenital anomaly/birth defect

#### **f. Other situations (Important Medical Event)**

An event that may not result in death, be immediately life-threatening, or require hospitalization, but may be considered serious when, based on appropriate medical judgment, the event may jeopardize the participant and may require medical or surgical intervention to prevent one of the outcomes listed in the above definition. Examples of such events include invasive or malignant cancers (excluding the disease[s] under study in oncology protocols), intensive treatment in an emergency department or at home for allergic bronchospasm, blood dyscrasias, or convulsions that do not result in hospitalization, or development of drug dependency or drug abuse.

For Japan, an event which may lead to disability is also considered as the important medical event. It includes a case that is exposed to a risk of dysfunction to an extent that interferes with daily life when the adverse drug reaction occurs. It does not include an adverse drug reaction that, had the reaction been more severe, may have caused disability.

### **9.3. Recording and Follow-Up of Adverse Events and/or Serious Adverse Events**

#### **Adverse Event and Serious Adverse Event Recording**

- An AE/SAE that begins or worsens after informed consent is signed should be recorded on the Adverse Event Form in the eCRF. Conditions that were present at the time informed consent was given should be recorded on the Medical History Form in the eCRF.
- When an AE/SAE occurs, it is the responsibility of the investigator to review all documentation (eg, hospital progress notes, laboratory reports, and diagnostics reports) related to the event.
- The investigator (or delegate) will then record all relevant AE/SAE information in the eCRF.
- It is **not** acceptable for the investigator to send photocopies of the participant's medical records in lieu of completing the AE eCRF page.
- There may be instances when copies of medical records for certain cases are requested. In this case, all participant identifiers, with the exception of the participant number, will be redacted on the copies of the medical records before submission.
- The investigator will attempt to establish a diagnosis of the event based on signs, symptoms, and/or other clinical information. Whenever possible, the diagnosis (not the individual signs/symptoms) will be documented as the AE/SAE. When a clear diagnosis cannot be identified, each sign or symptom should be reported as a separate AE/SAE.

To the extent possible, each AE/SAE should be evaluated to determine:

- The severity grade (CTCAE Grade 1 to 5). See below for further instructions on the assessment of intensity.
- Whether there is at least a reasonable possibility that the AE is related to the study drug: suspected (yes) or not suspected (no). See below for further instructions on the assessment of causality.
- The start and end dates, unless unresolved at final follow-up.
- The action taken with regard to study drug as a result of the AE/SAE(s).
- The event outcome (eg, not recovered/not resolved, recovered/resolved, recovering/resolving, recovered/resolved with sequelae, fatal, unknown).
- The seriousness, as per the SAE definition provided in Section 9.2.
- The action taken with regard to the event. Note: If an AE is treated with a concomitant medication or nondrug therapy, this action should be recorded on Adverse Event Form and the treatment should be specified on the appropriate eCRF (eg, Prior/Concomitant Medications, Procedures and Non-Drug Therapy).

### Assessment of Intensity

The severity of AEs will be assessed using CTCAE v5.0 Grades 1 through 5. If an event is not classified by CTCAE, the severity of the AE will be graded according to the scale below to estimate the grade of severity:

The investigator will make an assessment of intensity for each AE and SAE reported during the study and assign it to 1 of the following categories:

- **Grade 1:** Mild; asymptomatic or mild symptoms; clinical or diagnostic observations only; treatment not indicated.
- **Grade 2:** Moderate; minimal, local, or noninvasive treatment indicated; limiting age appropriate activities of daily living.
- **Grade 3:** Severe or medically significant but not immediately life-threatening; hospitalization or prolongation of hospitalization indicated; disabling; limiting self-care activities of daily living.
- **Grade 4:** Life-threatening consequences; urgent treatment indicated.
- **Grade 5:** Fatal.

### Assessment of Causality

- The investigator is obligated to assess the relationship between study treatment and each occurrence of each AE/SAE. If reference therapy is used in combination with an Incyte study drug or multiple Incyte study drugs are used, the relationship to each study drug must be assessed (ie, for the Incyte product(s) and for the other product(s) that is used in combination with the Incyte product). If appropriate, the relationship to the combination may be assessed as well.
- A "reasonable possibility" of a relationship conveys that there are facts, evidence, and/or arguments to suggest a causal relationship, rather than that a relationship cannot be ruled out.
- The investigator will use clinical judgment to determine the relationship.
- The investigator will also consult the RSI in the IB and/or Product Information, for marketed products, in his/her assessment.
- Alternative causes, such as underlying disease(s), concomitant therapy, and other risk factors, as well as the temporal relationship of the event to study treatment administration, will be considered and investigated.
- For each AE/SAE, the investigator **must** document in the medical notes that he/she has reviewed the AE/SAE and has provided an assessment of causality.
- With regard to assessing causality of SAEs:
  - There may be situations in which an SAE has occurred and the investigator has minimal information to include in the initial report. However, the causality assessment is one of the criteria used when determining regulatory reporting requirements. **Therefore, it is very important that the investigator always make an assessment of causality for every event before the initial transmission of the SAE.**
  - The investigator may change his/her opinion of causality in light of follow-up information and send a follow-up SAE report with the updated causality assessment.

### Follow-Up of Adverse Events and Serious Adverse Events

- The investigator is obligated to perform or arrange for the conduct of supplemental measurements and/or evaluations as medically indicated or as requested by the sponsor to elucidate the nature and/or causality of the AE or SAE as fully as possible. This may include additional laboratory tests or investigations, histopathological examinations, or consultation with other health care professionals.
- New or updated information will be recorded in the originally completed eCRF.
- Any updated SAE data will be submitted to the sponsor (or designee) within 24 hours of receipt of the information.
- Once an AE is detected, it should be followed until it has resolved or until it is judged to be permanent; assessment should be made at each visit (or more frequently if necessary) of any changes in severity, the suspected relationship to the study drug, the interventions required to treat the event, and the outcome.
- When the severity of an AE changes over time for a reporting period (eg, between visits), each change in severity will be reported as a separate AE until the event resolves.

### 9.4. Reporting of Serious Adverse Events

Regardless of suspected causality (eg, relationship to study drug or study procedure[s]), all SAEs occurring after the participant has signed the ICF through 35 days after the last dose of study treatment **or** until the participant starts a new anticancer therapy, whichever occurs earlier) must be reported to the sponsor (or designee) within **24 hours** of learning of its occurrence, unless otherwise specified by the Protocol. The investigator will submit any updated SAE data to the sponsor (or designee) within 24 hours of it being available. For Japan, this information must also be reported immediately to the head of the study site.

Investigators are not obligated to actively seek AE or SAE information after conclusion of the study participation. However, if the investigator learns of any SAE, including a death, at any time after a participant has been discharged from the study, and he/she considers the event to be reasonably related to the study treatment or study participation, the investigator must notify the sponsor (or designee) within 24 hours of becoming aware of the event.

After the initial AE/SAE report, the investigator is required to proactively follow each participant at subsequent visits/contacts. All SAEs will be followed until resolution, stabilization, the event is otherwise explained, or the participant is lost to follow-up (as defined in Section [7.3](#)).

Prompt notification by the investigator to the sponsor of a SAE is essential so that legal obligations and ethical responsibilities towards the safety of participants and the safety of a study treatment under clinical investigation are met.

If the SAE is not documented in the [IB](#) or the study drug (new occurrence) and is thought to be related to the sponsor's study drug, the sponsor or its designee may urgently require further information from the investigator for reporting to health authorities. The sponsor or its designee may need to issue an Investigator Notification to inform all investigators involved in any study with the same drug that this SAE has been reported. Suspected Unexpected Serious Adverse Reactions will be collected and reported to the competent authorities and relevant ethics committees in accordance with Directive 2001/20/EC, or as per national regulatory requirements

in participating countries. For Japan, suspected expected deaths and life-threatening events will also be reported to the PMDA as per local regulatory requirements.

The sponsor has a legal responsibility to notify both the local regulatory authority and other regulatory agencies about the safety of a study treatment under clinical investigation. The sponsor will comply with country-specific regulatory requirements relating to safety reporting to the regulatory authority, IRB/IEC, and investigators.

Investigator safety reports must be prepared for suspected unexpected adverse reactions according to local regulatory requirements and sponsor policy and forwarded to investigators as necessary.

An investigator who receives an investigator safety report describing a SAE or other specific safety information (eg, summary or listing of SAEs) from the sponsor will review and then file it along with the **IB** and will notify the IRB/IEC, if appropriate according to local requirements.

#### **Serious Adverse Event Reporting**

- Information about all SAEs is collected and recorded on the Adverse Event Form in the eCRF.
- The investigator must also complete the Incyte Serious Adverse Event Report Form, in English. Refer to the Incyte Reference Guide for Completing the Serious Adverse Event Report Form.
- Facsimile or email transmission of the Serious Adverse Event Report Form is the preferred method to transmit this information to the PhV/designee (eg, C3i/Telerx). The contact information of the sponsor's study-specific representatives is listed in the Study Reference Manual provided to each site. The original copy of the Serious Adverse Event Report Form and the confirmation sheet must be kept at the study site.
- Follow-up information is recorded on an amended or new Serious Adverse Event Report Form, with an indication that it is follow-up to the previously reported SAE and the date of the original report. The follow-up report should include information that was not provided on the previous Serious Adverse Event Report Form, such as the outcome of the event (eg, resolved or ongoing), treatment provided, action taken with study drug because of the SAE (eg, dose reduced, interrupted, or discontinued), or participant disposition (eg, continued or withdrew from study participation). Each recurrence, complication, or progression of the original event should be reported as follow-up to that event, regardless of when it occurs.
- In rare circumstances and in the absence of facsimile or computer equipment, notification by telephone is acceptable with a copy of the Incyte Serious Adverse Event Report Form sent by overnight mail or courier service. Initial notification via telephone does not replace the need for the investigator to complete and sign the Serious Adverse Event Report Form within the designated reporting timeframes.
- Contacts for SAE reporting can be found in the Study Manual.
- For Japan, any SAE relating to phosphate binders that were used for treatment of hyperphosphatemia should also be reported in the same manner.

## 9.5. Pregnancy

Pregnancy, in and of itself, is not regarded as an AE unless there is suspicion that study drug may have interfered with the effectiveness of a contraceptive medication or method. When a pregnancy has been confirmed in a participant during maternal or paternal exposure to study drug, the following procedures should be followed in order to ensure safety:

- The study treatment must be interrupted immediately (female participants only).
- If the female participant is no longer pregnant and meets the treatment continuation criteria within 28 days of the scheduled start of a cycle (or your maximum allowable time off study drug), study treatment may be resumed after approval has been received from the sponsor medical monitor. (Further note: Careful considerations should be taken regarding the anticoagulant properties of the study drug(s) and potential bleeding risks associated with restarting to determine if this is a viable addition to your Protocol.)
- The investigator must complete and submit the Incyte Clinical Trial Pregnancy Form to the sponsor or its designee within **24 hours** of learning of the pregnancy.

Data on fetal outcome are collected for regulatory reporting and drug safety evaluation. Follow-up should be conducted for each pregnancy to determine outcome, including spontaneous or voluntary termination, details of the birth, and the presence or absence of any birth defects, congenital abnormalities, or maternal and/or newborn complications, by following until the first well-baby visit. Pregnancy should be recorded on a Clinical Trial Pregnancy Form and reported by the investigator to the sponsor or its designee. Pregnancy follow-up information should be recorded on the same form and should include an assessment of the possible causal relationship to the sponsor's study drug to any pregnancy outcome, as well as follow-up to the first well-baby visit or the duration specified in local regulations, whichever is later. Refer to the Incyte Reference Guide for Completing the Clinical Trial Pregnancy Form.

**Any SAE occurring during pregnancy of a study participant must be recorded on the Serious Adverse Event Report Form and submitted to the sponsor or designee.**

Abnormal pregnancy outcomes (eg, spontaneous abortion, fetal death, stillbirth, congenital anomalies, or ectopic pregnancy) are considered SAEs (if occurring in the study participant) and must be reported as described in Section 9.4. If an abnormal pregnancy outcome is reported in a study participant's partner, the event should be reported to the sponsor on the Clinical Trial Pregnancy Form.

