## 7. DISCONTINUATION OF STUDY TREATMENT AND PARTICIPANT DISCONTINUATION/WITHDRAWAL

### 7.1. Discontinuation of Study Treatment

#### 7.1.1. Reasons for Discontinuation

Participants **must** be discontinued from study treatment for the following reasons. Please note that if a participant discontinues study treatment for reasons other than disease progression or withdraw of consent, the participant should be followed until disease progression is documented.

- The participant becomes pregnant.
- Consent is withdrawn.  
Note: Consent withdrawn means that the participant has explicitly indicated that they do not want to be followed any longer; in this case no further data, except data in public domain, may be solicited from or collected on the participant. Participants may choose to discontinue study treatment and remain in the study to be followed for progression and survival.
- Further participation would be injurious to the participant's health or well-being, in the investigator's medical judgment.
- Unacceptable toxicity as noted in Section 6.5.
- The study is terminated by the sponsor.
- The study is terminated by the local health authority, IRB, or IEC.
- Disease progression has been reported by central radiology review.
- Other antineoplastic treatment is initiated, not including palliative radiation.

A participant **may** be discontinued from study treatment if a participant is noncompliant with study procedures or study drug/treatment administration in the investigator's opinion, the sponsor should be consulted for instruction on handling the participant.

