#### 7.1.2. Discontinuation Procedures

In the event that the decision is made to permanently discontinue the study treatment, the EOT visit should be conducted. Reasonable efforts should be made to have the participant return for a follow-up visit. These visits are described in [Table 3](#) and [Table 4](#). The last date of the last dose of study drug(s)/treatment and the reason for discontinuation of study treatment will be recorded in the eCRF.

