#### If a participant is discontinued from study treatment:

- The study monitor or sponsor must be notified.
- The reason(s) for withdrawal must be documented in the participant's medical record and the primary reason for withdrawal must be included in the eCRF.
- The EOT visit should be performed.

- The date of the EOT visit should be recorded in the IRT.
- Participants must be followed for safety until the time of the follow-up visit or until study drug/treatment-related toxicities resolve, return to baseline, or are deemed irreversible, whichever is longest.

If the participant discontinues study treatment and actively withdraws consent for collection of follow-up data (safety follow-up or disease assessment), then no additional data collection should occur; however, participants will have the option of withdrawing consent for study treatment but continuing in the follow-up period of the study for safety/efficacy assessments and survival follow-up.

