### **8.3.6.1. Pregnancy Testing**

[figure not shown]
A serum pregnancy test will be required for all women of childbearing potential during screening and at the EOT visit; participants going into hospice are not required to provide EOT pregnancy test. Urine pregnancy tests will be performed locally on Day 1 of each cycle, as outlined in [Table 4](#), as medically indicated (eg, in case of loss of menstrual cycle, when pregnancy is suspected), or per country-specific requirement (note that country-required urine pregnancy testing will be outlined and communicated to investigational sites under separate cover). If a urine pregnancy test is positive, the results should be confirmed with a serum pregnancy test.

If the serum pregnancy test is negative after a urine test was positive, the investigator will assess the potential benefit/risk to the participant and determine whether it is in the participant's best interest to resume study drug and continue participation in the study.

If a pregnancy is confirmed by a serum pregnancy test, see Section [9.5](#) for reporting requirements.

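### Two safety rules conflict within the protocol: Section 9.5 lets treatment resume after a confirmed pregnancy although 7.1.1 requires discontinuation, and Section 8.3.4 allows entry above the 480 ms limit in exclusion 14 with no ceiling

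*Protocol*

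**What the plan says.** **Pregnancy.** Section 7.1.1 of the protocol says that participants must "be discontinued from study treatment for the following reasons", and the first entry on that list is "The participant becomes pregnant". Section 7.1.2 explains what discontinuation involves: "In the event that the decision is made to permanently discontinue the study treatment, the EOT visit should be conducted". Its checklist for a discontinued participant repeats the step: "The EOT visit should be performed".

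Section 9.5 sets out what to do once a pregnancy is confirmed: "The study treatment must be interrupted immediately (female participants only"). The next bullet is a restart rule for a woman whose pregnancy has ended and who again qualifies for treatment. It gives a 28-day window, counted from the planned cycle start, and its central clause reads: "(or your maximum allowable time off study drug), study treatment may be resumed after approval has been received from the sponsor medical monitor". A bracketed note follows. It asks the author to weigh the drug's anticoagulant properties and bleeding risk, and to decide whether the text is worth including in the protocol.

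Section 8.3.6.1 directs sites between these texts: "If a pregnancy is confirmed by a serum pregnancy test, see Section" 9.5, for reporting requirements. It has a separate provision that begins "If the serum pregnancy test is negative after a urine test was positive". There the investigator weighs benefit and risk and may resume drug.

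**QTc at entry.** Exclusion 14 (Section 5.2) excludes a screening QTcF above 480 ms. Its one medical monitor route is the use of JTc when QRS exceeds 120 ms, and JTc must then be 340 ms or less. Section 5 states that waivers of, and exemptions from, the enrollment criteria are not allowed. Section 8.3.4 says that a participant with a single screening QTc above 480 ms may enroll on either of two grounds: a three-ECG average of 480 ms or less, or the medical monitor's approval.

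**The concern.** In each case one section grants what another withholds. For pregnancy, the question is whether a woman is given study drug again after a confirmed pregnancy. For QTc, it is whether someone above the stated entry limit is dosed at all. An investigator, a medical monitor or an inspector could cite protocol text for either answer, and nothing in the protocol says which text governs. The pregnancy conflict is likely to be met in practice, because 8.3.6.1 sends confirmed cases to 9.5, which holds the permissive text.

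**Working it through.** No arithmetic applies. The check sets current protocol text side by side; amendment history is not used.

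| Question | Stricter text | Permissive text | Anything linking them? |
|---|---|---|---|
| Drug after a confirmed pregnancy | 7.1.1: must be discontinued, no exception | 9.5: interrupted; may resume with medical monitor approval | 7.1.1 does not mention 9.5, and 9.5 does not mention 7.1.1 |
| Entry with QTc above 480 ms | Exclusion 14: excluded. Section 5: no waivers | 8.3.4: may enroll with medical monitor approval, no ceiling | Exclusion 14 does not mention this route |

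**Pregnancy, step by step.**
1. Could discontinuation in 7.1.1 mean a pause? Section 7.1.2 attaches the EOT visit to discontinuation and describes the decision as permanent. Section 8.7 also ties the EOT visit to permanent discontinuation. So it is not a pause.
2. Does 9.5 describe the same event? Yes. It applies when a pregnancy has been confirmed in a participant. It interrupts treatment and then gives conditions for restarting.
3. Does the false-positive provision in 8.3.6.1 reconcile them? No. It covers a positive urine test followed by a negative serum test, so no pregnancy is confirmed. It conflicts with neither section.
4. Was the restart a deliberate choice? The wording gives no sign of it. It addresses a protocol author (a maximum time off drug described as yours). It refers to anticoagulant properties, although Section 2.1 describes pemigatinib as an FGFR kinase inhibitor and the public text gives it no such property. It also leaves open whether the bullet belongs in the protocol.

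**QTc, step by step.**
1. The three-ECG average can be read as the way to establish the screening value. On that reading it agrees with exclusion 14, which only lacks a reference to it.
2. Approval is joined to the average by an *or*, so it is available when the average is also above 480 ms. No upper value is given.
3. The JTc route shows how the protocol handles an intended exception: it is written into exclusion 14, needs medical monitor approval and is capped at 340 ms. The approval route in 8.3.4 has neither an entry in exclusion 14 nor a cap.
4. Read with exclusion 14 and Section 5, the approval clause works as a waiver of the 480 ms limit.

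**The case against.** **The specific section governs the general one.** On this view 9.5 is the detailed pregnancy rule and qualifies 7.1.1. That would carry weight if 7.1.1 allowed exceptions or if 9.5 were finished text. Neither is so. Resumption may still be what the sponsor wants, and the fix leaves room for it.

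**A route written in the protocol is not a deviation.** Section 5 bars prospective approval of deviations, and following 8.3.4 is arguably not one. Medical monitor approval also appears within eligibility elsewhere: exclusion 6 for radiation fibrosis, and the JTc route. This stands in part. The QTc fault is then narrower: exclusion 14 omits the route, and the route has no limit. Both still need correcting.

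**Safeguards exist.** A reader might infer that sites can restart drug, or enroll above 480 ms, on their own authority. They cannot, because both permissions require the medical monitor. Restart also requires that the participant is no longer pregnant and meets continuation criteria. At entry, investigator judgment under exclusions 14 and 24 still applies. This objection stands, and it limits the harm to conflicting rules.

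Three further inferences are not supported:
- *That the 28 days in 9.5 breach the 14-day delay limit in 6.5.1.* The 14 days apply to toxicity and can be extended with the sponsor (6.5.1, 6.5.4). The 28 days are counted from a scheduled cycle start.
- *That three ECGs cannot be obtained because 8.3.4 schedules a single one.* The same section permits additional ECGs as clinically indicated.
- *That the three step-downs after up-titration (6.5.1) contradict the limit of two reductions per AE (6.5.4).* Steps taken for different AEs satisfy both, so this is not part of the point.

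**Conclusion.** The protocol is wrong as written on both matters. The pregnancy conflict is the clearer one: mandatory discontinuation in 7.1.1 against interruption and restart in 9.5, in a bullet that still carries drafting notes. The QTc conflict is smaller: an approval route without a ceiling that the exclusion criterion does not contain and that sits badly with the no-waiver rule.

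The size is qualitative. The documents do not give the number of women of childbearing potential, the pregnancy rate or the distribution of screening QTc, so the number affected cannot be derived. The primary ORR analysis, power and alpha are unaffected. The conclusion rests on reading discontinuation in 7.1.1 as permanent, which 7.1.2 and 8.7 support, and on reading the *or* in 8.3.4 as a true alternative. The documents do not settle which rule the sponsor intended in either case.

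**What to change.** **Section 9.5.** Replace the interruption bullet with: *Study treatment must be stopped immediately and permanently discontinued (female participants only; see Section 7.1.1).* Keep the word *immediately*, because 7.1.1 states no timing. Delete the resumption bullet and its note. Leave the urine-positive, serum-negative provision in 8.3.6.1 unchanged. If the sponsor does intend resumption, write it as an explicit exception in 7.1.1 with one stated maximum off-drug period, and still delete the template text.

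**Section 8.3.4 and exclusion 14.** Delete the medical monitor approval clause from 8.3.4. If the sponsor intends that route, write it into exclusion 14 with a stated QTcF ceiling, as is done for JTc. In either case, cross-reference the three-ECG average in exclusion 14 as the method for establishing screening QTcF. Leave the JTc route as it is.

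**Cost.** Wording changes in 9.5 (or 7.1.1), 8.3.4 and exclusion 14, with the IRB/IEC approval that Section 11.1 requires for amendments, and a notification to sites. Sample size, endpoints and analyses do not change.
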